5.3.1.8 Storage

At the study site, all investigational study drugs will be stored in a locked, safe area to prevent unauthorized access.

The study drug should be stored at room temperature away from direct sunlight and protected from excessive heat and cold.

5.3.1.9 Unused study drug supplies

Any unused Revlimid® (lenalidomide) should be returned as instructed through the Revlimid REMSTM program.

5.3.1.10 Prescribing Information

Lenalidomide (Revlimid®) will be provided to research subjects for the duration of their participation in this trial at no charge to them or their insurance providers. Lenalidomide will be provided in accordance with the Revlimid REMS TM program of Celgene Corporation. Per standard Revlimid REMSTM program requirements, all physicians who prescribe lenalidomide for research subjects enrolled into this trial, and all research subjects enrolled into this trial, must be registered in and must comply with all requirements of the Revlimid REMSTM program. Drug will be shipped on a per patient basis by the contract pharmacy to the clinic site for IND studies. Only enough lenalidomide for one cycle of therapy will be supplied to the patient each cycle.

Further information about the Revlimid REMS® program is available at www.celgeneriskmanagement.com.

5.3.1.11 Pregnancy Testing

Females must follow pregnancy testing requirements as outlined in the Revlimid REMS® program.

5.3.2 DESCRIPTION of Rituximab

Rituxan® (rituximab) is a monoclonal antibody directed against the CD20 antigen on B-lymphocytes. CD20 regulates cell cycle initiation; and, possibly, functions as a calcium channel.

5.3.2.1 CLINICAL PHARMACOLOGY

Mechanism of Action:

Rituximab binds to the antigen on the cell surface, activating complement-dependent cytotoxicity; and to human Fc receptors, mediating cell killing through an antibody-dependent cellular toxicity.

5.3.2.2 Pharmacokinetics and Drug Metabolism:

Absorption:

Rituximab is administered intravenously.

Pharmacokinetic Parameters:

Metabolism and Excretion:

Rituximab remains detectable in the serum for 3-6 months after completion of treatment with B-cell recovery beginning about 6 months following completion of treatment. Median B-cell levels return to normal by 12 months after completion of therapy. Once infused, absorption is

immediate and results in rapid and sustained depletion of circulating and tissue-based B cells. The half-life of rituximab at doses >100 mg/m2 is 4.4 days (range of 1.6-10.5 days). At doses of 375 mg/m2, the half life is 50 hours following the first dose to 174 hours following the fourth dose). The mechanism of clearance for rituximab is uncertain although phagocytosis and catabolism in the reticuloendothelial system is suspected.

5.3.2.3 Supplier(s)

Genentech Pharmaceuticals, Inc. Commercial rituximab for intravenous administration will be obtained from the UC Davis Cancer Center pharmacy or participating site's pharmacy and billed to the patient or a third party payer.

5.3.2.4 Dosage form

Rituximab is supplied as a sterile, colorless, preservative-free liquid concentrate for intravenous (IV) administration. Rituximab is supplied at a concentration of 10 mg/ml in either 100 mg (10 mL) or 500 mg (50 mL) single-use vials. The product is formulated for IV administration in 9 mg/mL sodium chloride, 7.35 mg/mL sodium citrate dehydrate, 0.7 mg/mL polysorbate 80, and sterile water for injection. The pH is adjusted to 6.5.

5.3.2.5 Storage

Unopened vials may be stored refrigerated. When diluted for infusion, the solutions are stable at 2-8 degrees C (36-46 degrees F) for 24 hours and at room temperature for an additional 12 hours.

5.4 Screening and Eligibility

The Investigator is responsible for keeping a record of all subjects who sign an Informed Consent Form for entry into the study. All subjects will be screened for eligibility. Screening procedures are outlined in Section 2, Schedule of Study Assessments and unless otherwise specified, must take place within 28 days prior to initiation of therapy. Screening pregnancy tests for women of child-bearing potential must occur 10-14 days and again \leq 24 hours from initiation of therapy.

Approximately 30 subjects with previously untreated indolent Non-Hodgkin's Lymphoma will be screened for enrollment and must meet the eligibility criteria below.

5.4.1 Inclusion Criteria

Subjects must meet the following inclusion criteria to be eligible for the study. (All responses to inclusion criteria should be YES)

- 1. All patients must be informed of the investigative nature of the clinical trial and give written informed consent in accordance with institutional and federal guidelines.
- 2. Age \geq 18 years at the time of signing the informed consent form.
- 3. Able to adhere to the study visit schedule and other protocol requirements.
- 4. Previously untreated, histologically confirmed indolent lymphoma including follicle cell lymphoma, WHO classification, grade I or II, and marginal zone lymphoma. Bone

marrow biopsies as the sole means of diagnosis are not acceptable, but they may be submitted in conjunction with nodal biopsies. Fine needle aspirates are not acceptable.

- 5. At least one measurable lesion according to the International Working Group Response criteria for lymphomas. There must be measurable lymphadenopathy to follow with serial exam and/or imaging.
- 6. Submission of original biopsy for review by hematopathologist at local institution.
- 7. ECOG performance status of 0 -2 at study entry. (see appendix II)
- 8. No major organ dysfunction with laboratory test results within these ranges:
 - Absolute neutrophil count $\geq 1000 / \text{uL}$
 - Platelet count $\geq 75 \times 10^9/L$
 - Total bilirubin $\leq 2.0 \text{ mg/dL}$.
 - HIV negative
 - Subjects must have calculated creatinine clearance ≥ 30ml/min by Cockcroft-Gault formula. See section below, "Dosing Regimen", regarding lenalidomide dose adjustment for calculated creatinine clearance ≥ 30ml/min and < 60ml/min.
- 9. Life expectancy of greater than 3 months.
- 10. All study participants must be registered into the mandatory Revlimid REMSTM program, and be willing and able to comply with the requirements of Revlimid REMSTM
- 11. Females of reproductive potential must adhere to the scheduled pregnancy testing as required in the Revlimid REMS® program. Females of childbearing potential (FCBP)[†] must have a negative serum or urine pregnancy test with a sensitivity of at least 50 mIU/mL within 10 14 days and again within 24 hours prior to prescribing lenalidomide for Cycle 1 (prescriptions must be filled within 7 days as required by Revlimid REMSTM) and must either commit to continued abstinence from heterosexual intercourse or begin TWO acceptable methods of birth control, one highly effective method and one additional effective method AT THE SAME TIME, at least 28 days before she starts taking lenalidomide. FCBP must also agree to ongoing pregnancy testing. Men must agree to use a latex condom during sexual contact with a FCBP even if they have had a successful vasectomy. See Appendix: Risks of Fetal Exposure, Pregnancy Testing Guidelines and Acceptable Birth Control Methods.

[†] A female of childbearing potential is a sexually mature woman who: 1) has not undergone a hysterectomy or bilateral oophorectomy; or 2) has not been naturally postmenopausal for at least 24 consecutive months (i.e., has had menses at any time in the preceding 24 consecutive months).

- 12. Disease free of prior malignancies for ≥ 4 years with exception of currently treated basal cell, squamous cell carcinoma of the skin, or carcinoma "in situ" of the cervix or breast.
- 13. Able to take aspirin (81 or 325 mg) daily as prophylactic anticoagulation. (Patient's intolerant to ASA may use low molecular weight heparin).
- 14. Must be able to swallow lenalidomide capsules.

Inclusion Criteria for Radiotherapy Cohort

- Enrolled on UCDCC#224 and progress through protocol therapy
- At least two measurable sites of disease according to the International Working Group Response criteria for lymphomas. There must be measurable lymphadenopathy to follow with serial exam and/or imaging, and one lesion must be suitable for local radiotherapy, with an additional lesion(s) to follow for response assessment.

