Response rate (overall and complete) in non-target lesions following local radiation with concurrent lenalidomide in patients previously refractory to the combination of lenalidomide and rituximab.

STUDY DESIGN:

The study will be a multi-institution, phase II clinical trial in patients with previously untreated indolent Non-Hodgkin's lymphoma. Patients will receive lenalidomide 20 mg daily, on days 1-21 of a 28 day cycle. Rituximab 375 mg/m2 will be administered weekly for 4 doses starting day 15 of cycle 1, to be repeated if patient does not achieve a complete response after cycle 4, on days 1, 8, 15 and 22 of cycle 5. Therapy with lenalidomide may be discontinued after twelve cycles if the patient achieves a complete response.

Patients progressing on lenalidomide and rituximab will be offered treatment in a radiotherapy cohort. Patients will continue lenalidomide at the current dose, on days 1-21 of a 28 day cycle. Local fractionated radiotherapy will be delivered to a single site of disease days 1-5 of a 28 day

cycle to 20 Gy in 4 Gy fractions. Re-staging will be performed every 2 months, and lenalidomide will be continued until disease progression or intolerance.

STUDY ENDPOINTS:

Primary:

Complete response (CR), near complete response (CRu), or partial response (PR), stable disease (SD) of 4 months.

Secondary:

Time to disease progression, tolerability, duration of response, overall survival, and tumor control rate from the start of treatment.

Measurement of immune profile

STUDY DURATION:	TOTAL SAMPLE SIZE:
Patients will be enrolled over 2yrs.	Approximately 30 patients
	Of the 30 total patients 10 progressing patients will be offered optional treatment on the radiotherapy arm
DOSING REGIMEN(S):	STUDY DRUG SUPPLIES:
Lenalidomide will be initiated at 20 mg daily, days 1-21 of a 28 day cycle, to be continued until disease progression, unacceptable toxicity or after twelve cycles if the patient has achieved a complete response. Rituximab 375 mg/m2/wk x 4 weeks, to begin Day 15 of cycle 1. After 4 cycles of therapy if patient	Celgene Corporation will supply lenalidomide as 5 mg capsules.
does not achieve CR, the patient will receive a second course of Rituximab.	
Blood samples for companion study to assess immune profiles will be obtained within 1 week	
prior to starting treatment & then on days 15, 30,	
60 and 120, and then at the end of treatment or	

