6.5 Radiation Therapy

6.5.1 Selection of a target lesion

All patients should have at least 2 measurable sites of disease (one target lesion and one or more lesions for response assessment). The target lesion for radiation should measure a minimum of 1 cm and a maximum of 8 cm in greatest diameter. The lesion least likely to result in normal tissue toxicity should generally be selected for treatment at investigator discretion. Suitable targets include lymph nodes and extranodal tumor deposits. CNS disease is NOT a suitable target and patients with CNS involvement are not eligible for enrollment.

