8.5 Relapsed Disease (after CR)/Progressive Disease (after PR, SD)

Lymph nodes should be considered abnormal if the long axis is more than 1.5 cm regardless of the short axis. If a lymph node has a long axis of 1.1 to 1.5 cm, it should only be considered abnormal if its short axis is more than 1.0. Lymph nodes ≤1.0 ≤1.0cm will not be considered as abnormal for relapse or progressive disease.

- 1. Appearance of any new lesion more than 1.5 cm in any axis during or at the end of therapy, even if other lesions are decreasing in size. Increased FDG uptake in a previously unaffected site should only be considered relapsed or progressive disease after confirmation with other modalities. In patients with no prior history of pulmonary lymphoma, new lung nodules identified by CT are mostly benign. Thus, a therapeutic decision should not be made solely on the basis of the PET without histologic confirmation.
- 2. At least a 50% increase from nadir in the SPD of any previously involved nodes, or in a single involved node, or the size of other lesions (eg, splenic or hepatic nodules). To be considered progressive disease, a lymph node with a diameter of the short axis of less than 1.0cm must increase by ≥ 50% and to a size of 1.5x1.5 cm or more than 1.5 cm in the long axis.
- 3. At least a 50% increase in the longest diameter of any single previously identified node more than 1 cm in its short axis.
- 4. Lesions should be PET positive if observed in a typical FDG avid lymphoma or the lesion was PET positive before therapy unless the lesion is too small to be detected with current PET systems (<1.5 cm in its long axis by CT).

Measurable extranodal disease should be assessed in a manner similar to that for nodal disease. For these recommendations, the spleen is considered nodal disease. Disease that is only assessable (eg, pleural effusions, bone lesions) will be recorded as present or absent only, unless, while an abnormality is still noted by imaging studies or physical examination, it is found to be histologically negative.

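### When the irradiated lesion is the only one progressing, a lesion already shrinking on lenalidomide can be scored as a distant response to radiotherapy

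*Combined protocol and SAP*

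**What the plan says.** Entry to the radiotherapy cohort is defined for the patient, not the lesion. Section 5.4.1 requires "Enrolled on UCDCC#224 and progress through protocol therapy" and at least two measurable sites, of which "one lesion must be suitable for local radiotherapy, with an additional lesion(s) to follow for response assessment". Section 6.5.1 repeats the count. On the choice of lesion to irradiate it says: "The lesion least likely to result in normal tissue toxicity should generally be selected for treatment at investigator discretion". Neither section says whether the lesions left for assessment must be new, growing or stable.

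Section 8.5 gives several routes to progression. One is a new lesion above a size limit, "even if other lesions are decreasing in size". Another is "At least a 50% increase from nadir in the SPD of any previously involved nodes, or in a single involved node".

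The synopsis lists as a secondary objective "Response rate (overall and complete) in non-target lesions following local radiation with concurrent lenalidomide", in patients refractory to the combination. Lenalidomide continues through the cohort (synopsis; section 5.3), which takes up to 10 patients. Footnote 20 to the schedule in section 2 calls for a scan documenting progression and another 2 months after radiotherapy. No section names the reference scan for response after radiotherapy or asks for each lesion's earlier trend. Section 11.3 calls this part exploratory, but says any documented response would count as significant and justify further study.

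**The concern.** The cohort asks whether local radiation, with lenalidomide continuing, produces a response at distant sites in patients whose disease has progressed on the combination. A lesion that was regressing before radiation, and goes on regressing under the same drug, carries no information on that question. There is no control group that would reveal the error. Because one response is enough for a positive conclusion, one misattributed lesion could decide what the cohort is taken to show. Main-study conclusions are not affected.

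**Working it through.** **1. Which situations are open.** The check is whether the conditions for partial response in section 8.3 stop a false distant response. That section uses the summed products of diameters of up to six dominant nodes, and also requires no increase in other nodes, liver or spleen and no new sites.

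| Situation at progression | Do the 8.3 conditions block a false response? |
|---|---|
| A non-irradiated lesion is growing and keeps growing | Yes, if 8.3 is applied to all non-irradiated disease |
| A non-progressing lesion is irradiated, so the progressing one stays under assessment | Usually, for the same reason |
| The irradiated lesion is the only progressing site and the others are shrinking | No |

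The third row is possible under sections 5.4.1, 6.5.1 and 8.5 as written. The confirmatory scan at least 4 weeks later (section 2, footnote 7) does not close it, because a drug-driven regression would also be confirmed.

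**2. Illustration (sizes assumed).**
- Irradiated node: 2.0 × 2.0 = 4.00 cm² at nadir, 2.5 × 2.5 = 6.25 cm² at progression. 6.25/4.00 − 1 = +56%, which is progression on a single node.
- Followed node: 4.0 × 4.0 = 16.00 cm² at study baseline, 3.0 × 3.0 = 9.00 cm² on the progression scan, 2.1 × 2.1 = 4.41 cm² at the next scan after radiation.
- Before radiation: 9.00/16.00 − 1 = −44%. After radiation: 4.41/9.00 − 1 = −51%.

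The followed node meets the 50% size criterion on a trend that predates radiation. Naming the progression scan as reference is necessary, but does not by itself remove the problem.

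**3. How long rituximab could contribute.** A second course goes to patients without a complete response after cycle 4 and ends on cycle 5 day 22 (section 6.1), which is study day 4 × 28 + 22 = 134. Section 5.3.2.2 states: "Rituximab remains detectable in the serum for 3-6 months after completion of treatment". With 30-day months that reaches day 134 + 90 = 224 (end of cycle 8) to day 134 + 180 = 314 (cycle 12). Residual rituximab is therefore possible for earlier progressors only.

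**4. Consequence for the one-response rule.** The plan states no error rate or response threshold for this cohort, so there is no figure to reproduce. Let q be the chance that a treated patient shows a false distant response with no radiation effect. The documents give no value for q, so all values below are assumptions. P(at least one in n) = 1 − (1 − q)^n.

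| q (assumed) | n = 10 | n = 5 |
|---|---|---|
| 1% | 1 − 0.99^10 = 9.6% | 1 − 0.99^5 = 4.9% |
| 5% | 1 − 0.95^10 = 40.1% | 1 − 0.95^5 = 22.6% |
| 10% | 1 − 0.90^10 = 65.1% | 1 − 0.90^5 = 41.0% |

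In reverse, a 5% chance of a false signal in 10 patients needs only q = 1 − 0.95^(1/10) = 0.5%.

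**The case against.** The strongest reply is that response is not scored on one convenient lesion. The second site in sections 5.4.1 and 6.5.1 is an eligibility minimum, while section 8.3 looks at up to six dominant nodes and fails a partial response if another node grows or a new site appears. This stands, and it narrows the concern mainly to patients whose only progressing site is irradiated. A reader might infer that any shrinking lesion can be credited whatever the rest of the disease does. Section 8.3 does not support that, provided it is applied to all non-irradiated disease.

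Several other limits also stand:
- Section 6.5.1 selects the irradiated lesion by expected toxicity, so the sole progressing site will not always be the one treated.
- The wording about other lesions decreasing belongs to the new-lesion route. For the single-node route, shrinkage elsewhere is permitted by silence, not stated.
- Detectable rituximab is not the same as active rituximab, and later progressors fall outside that window.
- q is a joint probability (mixed progression, sole progressing site irradiated, no growth or new site elsewhere, and a further reduction large enough for response), and nothing in the documents fixes it.

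The stakes are modest too. The cohort is optional, uncontrolled and exploratory. Section 5.1.2 lists only immune correlates after radiotherapy, and distant response appears as an objective only in the synopsis. No lesion rule can isolate a radiation effect without a control. But the exploratory label does not remove the rule that one response suffices, and a bias that existing scans can identify is worth removing.

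**Conclusion.** The gap is real but bounded. As written, the plan lets an ongoing drug response count as a distant response to radiotherapy, chiefly when the irradiated lesion is the only progressing one. One such case would satisfy section 11.3. For assumed rates of 1% to 10% the chance of at least one is 9.6% to 65% with 10 patients and 4.9% to 41% with 5. These figures assume independent patients with a common q. They show how sensitive the rule is, and do not estimate how often the error would occur.

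A reader might also infer that only new or enlarged lesions should count. The documents do not require that: refractoriness is defined per patient, and a stable lesion was not already responding when radiation began. Discarding stable lesions would shrink a denominator of 10 or fewer with no matching gain. The correction should be made, but it is a matter of analysis and reporting and calls for no change in who enters the cohort.

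**What to change.** Add to sections 8 and 11.3, with a cross-reference from 5.4.1 and 6.5.1:

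1. Assess distant response on all non-irradiated measurable disease, with the progression (pre-radiation) scan as reference. The section 8.3 conditions on growth and new sites apply to all of that disease.
2. For each non-irradiated lesion, record the trend from the preceding scan to the progression scan as new, grown, unchanged or smaller, using a measurement tolerance fixed in advance. Record the interval between the two scans, since restaging is less frequent after a confirmed complete response.
3. Count a response towards the section 11.3 rule only if it rests on lesions that were not already smaller on the progression scan.
4. Report responses in already-shrinking lesions separately.
5. Give the distant-response rate twice: over all treated patients and over evaluable patients (those with at least one non-irradiated lesion not already smaller).

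This needs some wording and one column on the existing Tumor Measurement Log. It uses scans the plan already schedules and changes nothing about who is treated. The downside is that a few of the up to 10 patients may not contribute an attributable response, and the reported distant-response rate may be lower.

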5.4.2 Exclusion criteria

- 1. Any prior treatment for Non-Hodgkin's Lymphoma.
- 2. Any serious medical condition, laboratory abnormality, or psychiatric illness that would prevent the subject from signing the informed consent form.
- 3. Pregnant or breast-feeding females. (Lactating females must agree not to breast feed while taking lenalidomide).
- 4. Any condition, including the presence of laboratory abnormalities, which places the subject at unacceptable risk if he/she were to participate in the study or confounds the ability to interpret data from the study.
- 5. Use of any other experimental drug or therapy within 28 days of baseline.
- 6. Known hypersensitivity to thalidomide or rituximab.
- 7. The development of erythema nodosum if characterized by a desquamating rash while taking thalidomide or similar drugs.
- 8. Any prior use of lenalidomide.
- 9. Concurrent use of other anti-cancer agents or treatments.
- 10. Known positive for HIV
- 11. Known active hepatitis, type A, B or C. Patients who are seropositive because of hepatitis B virus vaccine are eligible.
- 12. Evidence for CNS metastatic disease
- 13. Subjects with \geq Grade 2 neuropathy

- 14. For Radiotherapy cohort, prior radiotherapy to the planned target lesion (prior radiotherapy to other sites of disease is permitted at investigator discretion)
- 15. For the radiotherapy cohort, CNS disease at the time of progression

5.5 Visit schedule and assessments

Screening Assessments and all on study scheduled visits and assessments are outlined in Section 2 Table of Study Assessments.

An unscheduled visit can occur at any time during the study. Source must be maintained for these unscheduled visits. The date for the visit and any data generated must be recorded on the appropriate CRF. Source documents for these unscheduled visits must also be maintained.

At treatment discontinuation, subjects will undergo off study evaluations per the Schedule of Assessments, Section 2. In addition, a safety assessment will be done approximately 30 days post the last dose of study drug. Follow-Up contact with the subjects should occur at a minimum of 4 weeks.

If the subject is in remission for more than 1 year then follow-up will be every four months unless there are clinical indications.

6 Treatment assignments

All patients will receive the treatment regimen outlined below.

